**Table 4. Dose Modification and Re-treatment Criteria for Oral and IV Study Drugs**

| Adverse Event  | Severity (CTCAE Grade)              | Oral Study Drug (rucaparib)    |                      | IV Study Drug (nivolumab)      |                                    |
|--|-------------------------------------|--------------------------------|----------------------|--------------------------------|------------------------------------|
|  |                                     | Dose Modification  | Re-treatment         | Dose Modification  | Re-treatment                       |
| ALT or AST > 3 × ULN AND bilirubin > 2 × ULN (suspected DILI)  |                                     | Hold               |                      | Discontinue                    |                                    |
| Creatinine elevations  | 2 (≥ 1.5 x baseline  ) | None                           | N/A                  | Hold                           | Grade ≤ 1 or baseline  |
| Creatinine elevations  | 3                                   | Hold                           | Grade 2  | Hold                           | Grade ≤ 1 or baseline  |
| Exception with nivolumab  |                                     |                                |                      |                                |                                    |
| Grade 3 lymphopenia or asymptomatic amylase or lipase  | 3                                   |                                |                      | None                           |                                    |
| Dosing-related  |                                     |                                |                      |                                |                                    |
| Any event that leads to delay in dosing lasting > 8 weeks from the previous dose requires discontinuation, with the exception of dosing delays to allow for prolonged steroid tapers to manage AEs. 
 
Dosing delays lasting > 8 weeks from the previous dose that occur for non-drug-related reasons may be allowed if approved by the study medical monitor/designee
 
 |                                     |                                |                      | Discontinue                    |                                    |
| Toxicity despite dose reduction steps to 200 mg BID or interruption of oral drug for > 14 consecutive days except if allowed if approved by the study medical monitor/designee. 
 
Prior to re-initiating treatment in a patient with a dosing delay > 14 days, the study medical monitor/designee must be consulted.
 
  |                                     | Discontinue                    |                      |                                |                                    |

Abbreviations: AE = adverse event; ALT = alanine aminotransferase; AML = acute myeloid leukemia; AST = aspartate aminotransferase; BID = twice daily; CTCAE = Common Terminology Criteria for Adverse Events; DILI = drug-induced liver injury; IV = intravenous; MDS = myelodysplastic syndrome; N/A = not applicable; ULN = upper limit of normal

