## 6. DOSING DELAYS/DOSE MODIFICATIONS

Doses of oral study drug (rucaparib), and/or IV study drug (nivolumab), may be interrupted or delayed for toxicity and other protocol-specified criteria. **Dose reductions are permitted for Rucaparib, but not for Nivolumab.** The assessment for delay or discontinuation should be made separately for the oral study drug (rucaparib) and the IV study drug (nivolumab) where class-specific safety profiles do not overlap; however, if toxicity is considered related to all study drugs or if the investigator is unable to determine which study drug is the cause of the AE, then all study drugs in the combination should be delayed and/or discontinued. For management of AEs which can be clearly attributed to rucaparib OR nivolumab, independent dose modification for either agent is allowed. If the relationship to an AE that is common to both drugs can be clearly distinguished, then a recommendation from the ET CCART for continuation of the non-offending drug can be requested by the investigator. Treatment may be prematurely discontinued due to withdrawal of consent, unacceptable toxicity, disease progression, completion of treatment cycles, or termination of the study, whichever occurs first.

Dose modification and re-treatment of oral and/or IV study drug are to be based on criteria presented in Table 4.

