| Laboratory abnormality except for those below that do not require delay                 | 4                      |   |                                    | Discontinue                    |                                    |
| Neutropenia ≤ 7 days  | 4                      |   |                                    | Hold                           | Grade ≤ 1 or baseline  |
| Lymphopenia or leukopenia   | 4                      |   |                                    | Hold                           | Grade ≤ 1 or baseline  |
| Laboratory Abnormalities   |                        |   |                                    |                                |                                    |
| Laboratory abnormality  | 3                      | Hold  | Grade 2                | Hold                           |                                    |
| ALT, AST, and/or bilirubin abnormalities  | 2                      | None  | N/A                                | Hold               | Grade ≤ 1 or baseline  |
| ALT/AST elevations  | 3                      | None, provided no signs of liver dysfunction  | N/A                                | Discontinue        |                                    |
| ALT/AST elevations  | 4                      | Hold  | ≤Grade 2 Reduce dose  | Discontinue                    |                                    |

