Patients may resume treatment with IV study drug when the drug-related AE(s) improve to Grade ≤ 1 or resolve to baseline value, with the following exceptions which are allowed: Grade 2 fatigue, Grade 2 skin toxicity (if no Grade 3 drug related skin AE). For patients with Grade 2 AST, ALT, or total bilirubin elevations, dosing may resume when laboratory values return to baseline and management with corticosteroids, if needed, is complete. Drug-related pulmonary toxicity, diarrhea or colitis must have resolved to baseline before treatment is resumed. Patients with persistent Grade 1 pneumonitis after completion of a steroid taper over at least 1 month may be eligible for retreatment if discussed with and approved by the study medical monitor. Patients with drug-related endocrinopathies adequately controlled with only physiologic hormone replacement may resume treatment after consultation with the study medical monitor. Adrenal insufficiency requires discontinuation regardless of control with hormone replacement.

The patient may continue at same or reduced dose at the discretion of the investigator. If treatment is resumed at the same dose, and the patient experiences the same toxicity, treatment should be interrupted, then resumed at a reduced dose following improvement of the event to ≤ CTCAE Grade 2. If the patient continues to experience toxicity, additional dose reduction steps are permitted; however, the investigator should consult with the sponsor's medical monitor before reducing to 300 mg BID.

In most cases of Grade 3 ALT or AST elevation, IV study drug will be permanently discontinued. For patients with Grade 3 ALT or AST elevations after the start of IV dosing, but on a background of previous elevations on the first cycle of oral study drug, IV study drug hold is required, but discontinuation is not required, if ALT/AST elevations begin to resolve before the next scheduled infusion, and toxicity is considered to be mainly related to oral study treatment, after the investigator discusses the case with the study medical monitor. Levels will be monitored every 3 days; if they continue to rise more than 20%, the Hepatic Adverse Event Management Algorithm for a Grade 3 event will be followed. Treatment with IV drug may be resumed if levels return to Grade 2. If total bilirubin elevations > 2 × ULN accompany any of the ALT/AST elevations, IV drug should be discontinued.

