| Starting Dose                              | 600 mg twice daily (each dose is two 300-mg tablets)                                | 1200 mg per day         |
| First Dose Reduction                       | 500 mg twice daily
(each dose is one 300-mg tablet and one 200-mg tablet) | 1000 mg per day         |
| Second Dose Reduction                      | 400 mg twice daily (each dose is two 200-mg tablets)                                | 800 mg per day          |
| Third Dose Reduction                       | 300 mg twice daily (each dose is one 300-mg tablet)                                 | 600 mg per day          |

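### Section 6 dosing rules conflict twice: rucaparib stops at a 200 mg BID level the dose table does not list, and Grade 2 adrenal insufficiency is both hold-and-re-treat and discontinue for nivolumab

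*Combined protocol and SAP*

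**What the plan says.** Section 6 states that "Dose modification and re-treatment of oral and/or IV study drug are to be based on criteria presented in Table 4".

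**Rucaparib.** The dosing-related part of Table 4 discontinues rucaparib for "Toxicity despite dose reduction steps to 200 mg BID", or for an interruption of more than 14 consecutive days unless the medical monitor approves. The dose-adjustment table after the footnotes starts at "600 mg twice daily (each dose is two 300-mg tablets") and lists three reductions, the last being "300 mg twice daily (each dose is one 300-mg tablet"). Footnote 4 governs re-treatment after most holds. After a first event, "The patient may continue at same or reduced dose at the discretion of the investigator". If the same toxicity returns after resumption at the same dose, "treatment should be interrupted, then resumed at a reduced dose". If toxicity continues, "additional dose reduction steps are permitted", with a medical monitor consultation before 300 mg BID. Footnote 4 names no lower dose. The Grade 4 ALT/AST row has its own rucaparib re-treatment rule, "Grade 2 Reduce dose", and cites footnote 10 (liver test monitoring), not footnote 4.

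**Nivolumab.** Among the Table 4 nivolumab exceptions, Grade 2 drug-related adrenal insufficiency or hypophysitis is a hold, with re-treatment at Grade 1 or lower, or baseline, under footnote 3. Grade 3 adrenal insufficiency is a discontinuation with an empty re-treatment cell. The last sentence of footnote 3 requires discontinuation for adrenal insufficiency whether or not hormone replacement controls it, and gives no grade. Footnote 6 states discontinuation for Grade 4 adrenal insufficiency or hypophysitis.

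**The concern.** A stopping rule has to give one answer for a given patient. The rucaparib row presupposes a fourth reduction that the dose table does not contain, so a patient with toxicity at 300 mg BID has not met the written toxicity trigger and has no listed dose to move to. One physician could stop and another could give 200 mg BID, and each could point to the text. For nivolumab, the Grade 2 adrenal cell permits re-treatment and the footnote attached to that cell forbids it.

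At stake are patient safety in a two-drug combination, consistent dosing, and whether a given decision can be judged compliant with the protocol. No claim is made about the primary PFS analysis.

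**Working it through.** The plan gives no statistical figure to reproduce here. The check is a comparison of the current rules, with simple arithmetic on the dose levels.

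**Rucaparib dose levels.** Daily dose = 2 × dose per intake; share = daily dose / 1200.

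| Level | Dose | mg per day | Share of start | In dose table? |
|---|---|---|---|---|
| Start | 600 mg BID | 1200 | 100% | yes |
| First reduction | 500 mg BID | 1000 | 83% | yes |
| Second reduction | 400 mg BID | 800 | 67% | yes |
| Third reduction | 300 mg BID | 600 | 600/1200 = 50% | yes, last row |
| (Fourth) | 200 mg BID | 400 | 400/1200 = 33% | no |

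Each listed step is 100 mg per intake (600 − 500 = 500 − 400 = 400 − 300), so 200 mg BID would be a fourth step. The two candidate floors differ by 600 − 400 = 200 mg per day, or 16.7 percentage points of the starting dose.

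**Which rule applies at 300 mg BID.**

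| Event at 300 mg BID | Governing text | Settled? |
|---|---|---|
| First event under a hold row citing footnote 4 | Same dose allowed on recovery | Yes |
| Same toxicity recurs after resumption at the same dose | Footnote 4: interrupt, then reduce | No: no lower dose listed, and the stopping trigger is at 200 mg BID |
| First Grade 4 ALT/AST elevation | Row's own rule: hold, then reduce; no same-dose option | No: same gap at the first event |
| Interruption of more than 14 days | Stop unless the medical monitor approves | Yes |

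**Adrenal insufficiency under nivolumab.**

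| Place | Grade | Instruction |
|---|---|---|
| Table 4, adrenal insufficiency or hypophysitis row | 2 | Hold; re-treat under footnote 3 |
| Table 4, adrenal insufficiency row | 3 | Discontinue; no re-treatment entry |
| Footnote 3, last sentence | none stated | Discontinue |
| Footnote 6 | 4 | Discontinue |
| Section 7.1.1, adrenal paragraph | 3 and 4 | Steroid treatment; refers back to section 6 |

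Footnote 3 is a re-treatment footnote. The Grade 3 adrenal row has nothing in its re-treatment cell and does not cite it, so the Grade 2 row is the only adrenal-specific row to which the sentence attaches. Read literally, it cancels the re-treatment that the cell allows. Section 7.1.1 does not break the tie: it covers only Grades 3 and 4 and returns the reader to section 6.

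**The case against.** On rucaparib, the dose table is headed as recommended adjustments and does not call 300 mg BID a minimum. Footnote 4 permits further steps and sets no floor. The 200 mg BID row is inside Table 4, which section 6 makes governing, and 200-mg tablets are already in use. On that view one table row is missing, and both gaps follow from it. This is a plausible reading and may be what was intended. It is not stated, however: the dose table ends at a row labelled the third reduction, and the only consultation tied to a dose level is before 300 mg BID.

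On adrenal insufficiency, the footnote 3 sentence closely echoes the Grade 3 row. It also follows a sentence about endocrinopathies controlled by hormone replacement, which matches a Grade 3 hold row that cites footnote 3. It can therefore be read as an exception at Grade 3, and an explicit Grade 2 row could be taken as more specific than a general footnote. Grade 3 or higher is probably the intended meaning, and footnote 6 is compatible with it. The sentence still carries no grade and is attached to the Grade 2 cell.

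On consequences, footnotes 1 and 2 let the investigator stop either drug on judgment, the medical monitor should already have been consulted before 300 mg BID, and the institution's data and safety monitoring committee reviews all adverse events. These safeguards limit harm. They do not say which written rule governs.

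**Conclusion.** Both conflicts are in the current text and should be fixed. The rucaparib toxicity trigger sits one unlisted step (100 mg per intake) below the last listed dose. This leaves two situations at 300 mg BID without a settled instruction: recurrent toxicity and a first Grade 4 ALT/AST elevation. The nivolumab conflict affects Grade 2 adrenal insufficiency.

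The documents give no rate for patients reaching 300 mg BID or for Grade 2 adrenal insufficiency, so no frequency is claimed. This is a correction for safety and consistent conduct; it does not touch the sample size or the primary analysis. The conclusion rests on reading the rules as written; the sponsor may have had one of the reconciling readings in mind.

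**What to change.** 1. **Rucaparib.** Either change the stopping row to 300 mg BID, or, if the sponsor intends the lower level, add 200 mg BID (one 200-mg tablet per intake, 400 mg per day) to the dose table as a fourth reduction. If 300 mg BID is the floor, state that recurrent toxicity or a Grade 4 ALT/AST elevation at that dose means discontinuing rucaparib.
2. **Nivolumab.** Either limit the last sentence of footnote 3 to Grade 3 or higher, or make Grade 2 adrenal insufficiency a discontinuation. The second option means splitting the Grade 2 row, because hypophysitis shares it.

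Two clerical items can go into the same amendment. The nivolumab entry in the Grade 3 ALT/AST row carries superscript 7 (hematology referral) where 5 appears intended, which should be checked against the source table. Footnote 11 refers to cohorts that this single-arm trial does not have.

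The cost is one protocol amendment to a few Table 4 cells, footnotes and possibly one dose-table row, with a notice to study staff. Sample size and analysis are unchanged.

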**Table 4. Dose Modification and Re-treatment Criteria for Oral and IV Study Drugs**

| Adverse Event | Severity (CTCAE Grade) | Oral Study Drug (rucaparib)    |              | IV Study Drug (nivolumab)      |              |
|---------------|------------------------|--------------------------------|--------------|--------------------------------|--------------|
|               |                        | Dose Modification  | Re-treatment | Dose Modification  | Re-treatment |

Oral drug may be discontinued for any AE, laboratory abnormality, or intercurrent illness which, in the judgment of the investigator, presents a substantial clinical risk to the patient with continued oral study treatment dosing. In addition, and at the discretion of the investigator, the dose of oral study drug may be held and/or reduced for Grade 2 toxicity not adequately controlled by concomitant medications and/or supportive care.

In addition to the criteria below, nivolumab should be held if there is any AE, laboratory abnormality, or intercurrent illness that, in the judgment of the investigator, warrants delaying the dose of study medication or discontinued if there is any AE, laboratory abnormality, or intercurrent illness that, in the judgment of the investigator, presents a substantial risk to the patient with continued IV study drug dosing. Patients who require dose hold should be re-evaluated weekly or more frequently if clinically indicated and resume dosing during the next scheduled dosing window (Cycle X, Day 1 ±3 days) after re-treatment criteria are met.

Patients may resume treatment with IV study drug when the drug-related AE(s) improve to Grade ≤ 1 or resolve to baseline value, with the following exceptions which are allowed: Grade 2 fatigue, Grade 2 skin toxicity (if no Grade 3 drug related skin AE). For patients with Grade 2 AST, ALT, or total bilirubin elevations, dosing may resume when laboratory values return to baseline and management with corticosteroids, if needed, is complete. Drug-related pulmonary toxicity, diarrhea or colitis must have resolved to baseline before treatment is resumed. Patients with persistent Grade 1 pneumonitis after completion of a steroid taper over at least 1 month may be eligible for retreatment if discussed with and approved by the study medical monitor. Patients with drug-related endocrinopathies adequately controlled with only physiologic hormone replacement may resume treatment after consultation with the study medical monitor. Adrenal insufficiency requires discontinuation regardless of control with hormone replacement.

The patient may continue at same or reduced dose at the discretion of the investigator. If treatment is resumed at the same dose, and the patient experiences the same toxicity, treatment should be interrupted, then resumed at a reduced dose following improvement of the event to ≤ CTCAE Grade 2. If the patient continues to experience toxicity, additional dose reduction steps are permitted; however, the investigator should consult with the sponsor's medical monitor before reducing to 300 mg BID.

In most cases of Grade 3 ALT or AST elevation, IV study drug will be permanently discontinued. For patients with Grade 3 ALT or AST elevations after the start of IV dosing, but on a background of previous elevations on the first cycle of oral study drug, IV study drug hold is required, but discontinuation is not required, if ALT/AST elevations begin to resolve before the next scheduled infusion, and toxicity is considered to be mainly related to oral study treatment, after the investigator discusses the case with the study medical monitor. Levels will be monitored every 3 days; if they continue to rise more than 20%, the Hepatic Adverse Event Management Algorithm for a Grade 3 event will be followed. Treatment with IV drug may be resumed if levels return to Grade 2. If total bilirubin elevations > 2 × ULN accompany any of the ALT/AST elevations, IV drug should be discontinued.

Such as, hyper- or hypothyroidism, or glucose intolerance, that resolve or are adequately controlled with physiologic hormone replacement (corticosteroids, thyroid hormones) or glucose-controlling agents, respectively, may not require discontinuation after discussion with and approval from the study medical monitor/designee. Grade 4 drug-related adrenal insufficiency or hypophysitis requires discontinuation regardless of control with hormone replacement.

If any blood parameters remain clinically abnormal > 4 weeks of dose interruption, the patient should be referred to hematologist for further investigations. Bone marrow analysis and/or blood cytogenetic analysis should be considered at this stage according to standard hematological practice.

For patients with Grade 2 ALT or AST elevations with onset after dosing of oral study drug, IV study treatment hold is not required if ALT/AST elevations begin to resolve before the next scheduled infusion and toxicity is considered to be mainly related to oral study treatment. If a subsequent ALT/AST increase of more than 20% is observed following infusion of IV study drug, the next IV study drug administration will be held and, if further increase is observed, the Hepatic Adverse Event Management Algorithm will be followed. In this case, IV study drug should be discontinued if Grade 2 elevations return post re-challenge. If total bilirubin elevations > 2 × ULN accompany any of the ALT/AST elevations, IV drug should be discontinued.

Bilirubin must be within normal limits and alkaline phosphatase must be < 3 x ULN. Monitor liver function tests weekly. If the patient has Grade 3 ALT/AST and continues on oral study drug, and levels do not decline within 2 weeks or they continue to rise, treatment interruption and improvement to ≤ Grade 2 will be required before oral study drug can be resumed, either at the current dose or at a reduced dose.

Monitor liver function tests weekly for 3 weeks after oral study drug has been restarted.

Grade 2 for nivolumab is described as ≥ 1.5 x baseline and baseline is the day the combination treatment starts (ie, Cycle 2 Day 1 in Cohort A1 and A2, and Cycle 1 Day 1 in Cohort B)

| RECOMMENDED DOSE ADJUSTMENTS FOR RUCAPARIB |   |                         |
|--|---|-------------------------|
|  | Dose   | Total mg per day |
| Starting Dose                              | 600 mg twice daily (each dose is two 300-mg tablets)                                | 1200 mg per day         |
| First Dose Reduction                       | 500 mg twice daily
(each dose is one 300-mg tablet and one 200-mg tablet) | 1000 mg per day         |
| Second Dose Reduction                      | 400 mg twice daily (each dose is two 200-mg tablets)                                | 800 mg per day          |
| Third Dose Reduction                       | 300 mg twice daily (each dose is one 300-mg tablet)                                 | 600 mg per day          |

